1. DEFINITION OF ADVERSE EVENTS

According to the E2A ICH guideline for Good Clinical Practice, an **adverse event** is any untoward medical occurrence in a patient or clinical investigation subject administered a pharmaceutical product and which does not necessarily have to have a causal relationship with this treatment.

An adverse event can therefore be:

- Any unfavorable and unintended sign (including an abnormal laboratory finding), symptom, or disease temporally associated with the use of a medicinal product, whether or not considered related to the medicinal product.

Events Meeting the AE Definition:

- Any deterioration in a laboratory value (hematology, clinical chemistry, or urinalysis) or other clinical test (e.g., ECG, X-ray) that is associated with symptoms or leads to a change in study treatment or concomitant treatment or discontinuation from study treatment.
- Exacerbation of a chronic or intermittent pre-existing condition, including either an increase in frequency and/or intensity of the condition.
- New conditions detected or diagnosed after study treatment administration even though it may have been present before the start of the study.
- Adverse events that are related to a protocol-mandated intervention, including those that occur prior to assignment of study treatment (e.g., screening invasive procedures such as biopsies).
- "Lack of efficacy" or "failure of expected pharmacological action" per se will not be reported as an AE or SAE. Such instances will be captured in the efficacy assessments. However, the signs, symptoms, and/or clinical sequelae resulting from lack of efficacy will be reported as AE or SAE if they fulfill the definition of an AE or SAE.

Events NOT Meeting the AE Definition (for Part 1):

- Any clinically significant abnormal laboratory findings or other abnormal safety assessments, unless judged by the Investigator to be more severe than expected for the participant's condition.
- Medical or surgical procedure (e.g., endoscopy, appendectomy): the condition that leads to the procedure is an AE.
- Situations where an untoward medical occurrence did not occur (social and/or convenience admission to a hospital).

- Anticipated day-to-day fluctuations of pre-existing disease(s) or condition(s) present or detected at the start of the study that do not worsen.

Events NOT Meeting the AE Definition (for Part 2):

- Any clinically significant abnormal laboratory findings or other abnormal safety assessments which are associated with the underlying disease, unless judged by the Investigator to be more severe than expected for the participant's condition.
- The disease being studied or expected progression, signs, or symptoms of the disease being studied, unless more severe than expected for the participant's condition.
- Medical or surgical procedure (e.g., endoscopy, appendectomy): the condition that leads to the procedure is an AE.
- Situations where an untoward medical occurrence did not occur (social and/or convenience admission to a hospital).
- Anticipated day-to-day fluctuations of pre-existing disease(s) or condition(s) present or detected at the start of the study that do not worsen.

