7.1 DISCONTINUATION OF STUDY TREATMENT

See the SoA (Section 1.3) for data to be collected at the time of treatment discontinuation and follow-up and for any further evaluations that need to be completed.

Participant must discontinue study treatment if they experience any of the following:

- Participant withdrawal of consent at any time.
- Any medical condition that the Investigator or Sponsor determines may jeopardize the participant's safety if he or she continues in the study.
- Investigator or Sponsor determines it is in the best interest of the participant.
- Pregnancy
- If stopping criteria are met (see Section 4.1.3)
- If non-compliance with study requirements as judged by the Investigator and consultation with the Sponsor.

Participants who discontinue study treatment prematurely will be asked to return to the clinic for a study completion/early termination visit (see Section 1.3) and may undergo follow-up assessments (see Section 1.3). The primary reason for premature study treatment discontinuation should be documented on the appropriate eCRF. Participants who discontinue study treatment prematurely can be replaced in both Parts 1 and 2.

Discontinuation of study intervention for abnormal liver function should be considered by the Investigator when a participant meets one of the conditions outlined in Section 6 of Appendix 3 or if the Investigator believes that it is in best interest of the participant.

If a clinically significant finding is identified (including, but not limited to changes from baseline in QT interval corrected using Fridericia's formula [QTcF]) after enrollment, the investigator or qualified designee will determine if the participant can continue in the study and if any change in participant management is needed. This review of the ECG taken at the time of collection must be documented. Any new clinically relevant finding should be reported as an AE.

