8.2.4 Clinical Safety Laboratory Assessments

Normal ranges for the study laboratory parameters must be supplied to the Sponsor before the study starts. A list of clinical laboratory tests to be performed is provided in [Appendix 4](#) and these assessments must be conducted in accordance with the separate laboratory manual and the SoA (Section 1.3).

The Investigator must review the laboratory report, document this review, and record any clinically relevant changes occurring during the study in the AE section of the CRF. The laboratory reports must be filed with the source documents. Clinically significant abnormal laboratory findings are those which are not associated with the underlying disease, unless judged by the Investigator to be more severe than expected for the participant's condition.

- In the event of unexplained abnormal clinically significant laboratory test values, the tests should be repeated immediately and followed up until they have returned to the normal range and/or an adequate explanation of the abnormality is found.
- If such values do not return to normal/baseline within a period of time judged reasonable by the Investigator, the etiology should be identified and the Sponsor notified.
- If laboratory values from non-protocol specified laboratory assessments performed at the local laboratory require a change in participant management or are considered clinically significant by the Investigator (e.g., SAE or AE or dose-modification) the results must be recorded in the CRF.

Results of clinical laboratory testing will be recorded in the eCRF or be received as electronically produced laboratory reports submitted directly from the central laboratory.

Additional blood or urine samples may be taken at the discretion of the Investigator if the results of any test fall outside the reference ranges, or clinical symptoms necessitate additional testing to monitor participant safety.

Where the clinical significance of abnormal lab results is considered uncertain, screening lab tests may be repeated before randomization to confirm eligibility.

If there is an alternative explanation for a positive urine or blood test for drugs of abuse, e.g., previous occasional intake of a medication or food containing for example, codeine, benzodiazepines or opiates, the test could be repeated to confirm washout.

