4. ABNORMAL LABORATORY VALUES

Not every laboratory abnormality qualifies as an adverse event. A laboratory test result should be reported as an adverse event if it meets any of the following criteria:

- Accompanied by clinical symptoms.
- Results in a change in study treatment (e.g., dosage modification, treatment interruption, or treatment discontinuation).
- Results in a medical intervention (e.g., potassium supplementation for hypokalemia) or a change in concomitant therapy.
- Clinically significant in the Investigator's judgment.

It is the Investigator's responsibility to review all laboratory findings. Medical and scientific judgment should be exercised in deciding whether an isolated laboratory abnormality should be classified as an adverse event.

If a clinically significant laboratory abnormality is a sign of a disease or syndrome (e.g., alkaline phosphatase and bilirubin 5 times the upper limit of normal [ULN] associated with cholecystitis), only the diagnosis (i.e., cholecystitis) should be recorded on the Adverse Event eCRF.

If a clinically significant laboratory abnormality is not a sign of a disease or syndrome, the abnormality itself should be recorded on the Adverse Event eCRF, along with a descriptor indicating if the test result is above or below the normal range (e.g., "elevated potassium", as opposed to "abnormal potassium"). If the laboratory abnormality can be characterized by a precise clinical term per standard definitions, the clinical term should be recorded as the adverse event. For example, an elevated serum potassium level of 7.0 mEq/L should be recorded as "hyperkalemia".

Observations of the same clinically significant laboratory abnormality from visit to visit should not be repeatedly recorded on the Adverse Event eCRF, unless the etiology changes. The initial severity of the event should be recorded, and the severity or seriousness should be updated any time the event worsens.

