5. ABNORMAL VITAL SIGN VALUES

Not every vital sign abnormality qualifies as an adverse event. A vital sign result should be reported as an adverse event if it meets any of the following criteria:

- Accompanied by clinical symptoms.
- Results in a change in study treatment (e.g., dosage modification, treatment interruption, or treatment discontinuation).
- Results in a medical intervention or a change in concomitant therapy.
- Clinically significant in the Investigator's judgment.

It is the Investigator's responsibility to review all vital sign findings. Medical and scientific judgment should be exercised in deciding whether an isolated vital sign abnormality should be classified as an adverse event.

If a clinically significant vital sign abnormality is a sign of a disease or syndrome (e.g., high blood pressure), only the diagnosis (i.e., hypertension) should be recorded on the Adverse Event eCRF.

Observations of the same clinically significant vital sign abnormality from visit to visit should not be repeatedly recorded on the Adverse Event eCRF, unless the etiology changes. The initial severity of the event should be recorded, and the severity or seriousness should be updated any time the event worsens.

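### In Part 1, Appendix 2 takes clinically significant laboratory and other safety findings out of the AE definition, while five other sections make them AEs

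*Combined protocol and SAP*

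**What the plan says.** Section 8.3 sends the site to Appendix 2 for the definition of an AE and to Appendix 3 for recording. The two appendices do not agree for Part 1.

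- **Appendix 2 Section 1, list of events that are not AEs, Part 1, first bullet:** "Any clinically significant abnormal laboratory findings or other abnormal safety assessments, unless judged by the Investigator to be more severe than expected", given that person's condition.
- **Same list, Part 2, first bullet:** "Any clinically significant abnormal laboratory findings or other abnormal safety assessments which are associated with the underlying disease", followed by the same exception. The limit to the underlying disease appears only here.
- **Section 8.2.4 (laboratory):** the Investigator must "record any clinically relevant changes occurring during the study in the AE section of the CRF".
- **Appendix 3 Section 4 (laboratory):** "A laboratory test result should be reported as an adverse event if it meets any of the following criteria". One of the criteria is "Clinically significant in the Investigator's judgment".
- **Appendix 3 Section 5 (vital signs):** "A vital sign result should be reported as an adverse event if it meets any of the following criteria", with clinical significance again on the list.
- **Section 7.1 (findings after enrollment, QTcF changes included):** "Any new clinically relevant finding should be reported as an AE".
- **Section 8.2.1 (physical examination):** new or worsened abnormalities of clinical significance go on the Adverse Event eCRF.

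None of the last five is confined to one part of the study, and no section gives an order of precedence.

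**The concern.** Clinical significance is what makes a finding an AE under Appendix 3. Under the Part 1 bullet it describes the class that is excluded. An Investigator who follows Appendix 2 and one who follows Appendix 3 can reach opposite answers on the same result, each with the protocol on their side.

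The incidence, severity and causality of AEs form the first item of the primary endpoint (Section 3), and Section 9.4.2 analyzes active participants by cohort. The type of finding affected is also one the protocol expects: Section 4.1.3 describes isolated transaminase rises as a recognized class effect. If classification varies within or between cohorts, differences in AE incidence across doses could partly reflect which section was followed.

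**Working it through.** The plan gives no figure to reproduce here. The check compares the texts and then bounds the reach.

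**Step 1: the rules side by side, for a new, clinically significant finding in a healthy volunteer with no symptoms and no treatment.**

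| Place | Finding type | AE? |
|---|---|---|
| Appendix 2 Section 1, Part 1 list | laboratory and other safety assessments | No, unless more severe than expected |
| Section 8.2.4 | laboratory | Yes |
| Appendix 3 Section 4 | laboratory | Yes |
| Appendix 3 Section 5 | vital signs | Yes |
| Section 7.1 | any new finding, ECG included | Yes |
| Section 8.2.1 | physical examination | Yes |

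Section 8.2.4 also describes clinically significant laboratory findings as those not linked to the underlying disease. The Part 1 bullet therefore removes the class that Section 8.2.4 tells the site to record. Appendix 2 Section 6 fits poorly with the bullet too: it counts isolated ALT/AST elevations below 5 x ULN in healthy participants among anticipated adverse events and exempts them only from expedited reporting.

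**Step 2: does the exception resolve it?** It asks whether the finding is worse than expected for the participant's condition. Part 1 participants must show no evidence of active or chronic disease (Section 5.1), and clinically significant laboratory abnormalities at screening and Day -1 are exclusionary (Section 5.2, Part 1 criterion 7). For most of them there is no clear condition to compare with. One Investigator may hold that any clinically significant abnormality exceeds what is expected in a healthy person, so the bullet excludes nothing. Another may hold that a transaminase rise described as a class effect and as anticipated is not more severe than expected, so the bullet excludes it. There are limited cases where a comparison is possible: Section 5.2 admits Gilbert's syndrome, asymptomatic gallstones and ALT below 1.5 x ULN.

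**Step 3: what other rules already capture.**

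- Appendix 2 Section 1 itself counts deteriorations that come with symptoms or lead to a change in study or concomitant treatment. Part 1 gives a single dose on Day 1, so after dosing only symptoms or concomitant treatment can trigger this.
- Section 4.1.3 names as dose-limiting AEs confirmed ALT/AST above 5 x ULN, the combinations above 3 x ULN with liver-function criteria or symptoms, confirmed eGFR below 60 ml/min, and Grade 3 or 4 laboratory abnormalities.
- Section 8.3.6 lists confirmed ALT/AST above 5 x ULN, and above 3 x ULN with bilirubin above 2 x ULN or jaundice, as events of special interest.
- Appendix 3 Section 6 requires AE reporting of ALT/AST above 3 x ULN combined with bilirubin, jaundice, INR/PT or symptom criteria.

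What remains is clinically significant findings that are asymptomatic, untreated and outside all of these. An isolated ALT between 3 and 5 x ULN, below Grade 3 and judged clinically significant, is an example.

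**Step 4: scale.** Inputs from Sections 9 and 9.2: four to five cohorts, each with 8 active and 2 placebo; Part 1 placebo pooled.

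- All active: 4 x 8 = 32 to 5 x 8 = 40. Pooled placebo: 4 x 2 = 8 to 5 x 2 = 10.
- Shift in the incidence of the specific AE term per participant reclassified = 1/n.
- One cohort, active: 1/8 = 12.5 percentage points.
- Pooled placebo: 1/10 = 10.0 to 1/8 = 12.5 points.
- All Part 1 active: 1/40 = 2.5 to 1/32 = 3.1 points.

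For overall AE incidence these are upper limits, because a participant with another AE is already counted.

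**The case against.** The best defense is that the exception works as intended: a new clinically significant abnormality in a healthy person is by nature more severe than expected, so it is an AE. Five other sections say so, and Appendix 2 Section 6 suggests that the sponsor reads it that way. The bullet also has some legitimate content, such as an expected bilirubin value in Gilbert's syndrome. This makes divergence less likely, but it relies on the reader overriding a listed exclusion. It also leaves that exclusion with almost nothing to exclude.

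Several stronger readings are tempting and are not supported:

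- *That the general AE definition contradicts the bullet.* It says that an AE can be "Any unfavorable and unintended sign (including an abnormal laboratory finding), symptom, or disease temporally associated with the use of a medicinal product". That is permissive and can stand beside an exclusion list.
- *That there is never a condition to judge against.* The conditions admitted by Section 5.2 show otherwise for a minority.
- *That all isolated transaminase rises below 5 x ULN escape AE recording.* Appendix 2 Section 6 treats them as AEs, and Appendix 3 Section 6 captures the combinations above 3 x ULN.
- *That a safety signal is lost.* Laboratory, vital-sign, ECG and physical findings are a separate item of the primary endpoint with their own listings and summaries (Sections 3, 9.4.2 and 9.4.2.1). Escalation review sees laboratory, ECG and vital-sign data directly (Section 4.1.2), and the liver, eGFR and Grade 3 or 4 laboratory stopping criteria use the values themselves.
- *That 12.5 points estimates the under-count.* It is only 1/8 and would apply to any recording question in a group of eight.

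The analysis is descriptive, with no hypothesis test (Section 9.1), so no test result depends on this.

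**Conclusion.** The point holds as an internal inconsistency that should be fixed. The Part 1 bullet in Appendix 2 Section 1 conflicts with Sections 8.2.4, 7.1 and 8.2.1 and with Appendix 3 Sections 4 and 5, and nothing settles which applies. The limit found only in the Part 2 bullet suggests a drafting slip when the list was split by part; that is inference.

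The consequence is confined to consistent recording in the Part 1 AE tables, for the residual group of findings described in the working. Each participant classified differently moves the incidence of that AE term by 12.5 percentage points in a cohort's active group and by 10 to 12.5 points in pooled placebo. These figures assume full cohorts of eight active and two placebo. No under-count rate can be derived from the documents, and none is claimed.

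**What to change.** In Appendix 2 Section 1, delete the first bullet of the Part 1 exclusion list. Little is lost, because the fourth bullet already covers expected fluctuations of pre-existing conditions that do not worsen. Alternatively, limit the first bullet to findings associated with a pre-existing condition recorded at baseline.

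In either case add one sentence: in Part 1, Appendix 3 Sections 4 and 5, together with Sections 8.2.4, 7.1 and 8.2.1, decide whether laboratory, vital-sign, ECG and physical findings are AEs.

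The cost is one bullet and one sentence. The downside is that some more AEs may be recorded in Part 1. The change concerns recording only.

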2. DEFINITION OF SERIOUS ADVERSE EVENTS

If an event is not an AE per definition above, then it cannot be a serious adverse event (SAE) even if serious conditions are met (e.g., hospitalization for signs/symptoms of the disease under study, death due to progression of disease).

A serious adverse event is defined as any untoward medical occurrence that at any dose:

- **Results in death.**
- **Is life-threatening.**
The term "life-threatening" in the definition of "serious" refers to an event in which the participant was at risk of death at the time of the event; it does not refer to an event which hypothetically might have caused death if it was more severe.
- **Requires inpatient hospitalization or prolongation of existing hospitalization** (see [Appendix 3](#)).

In general, hospitalization signifies that the participant has been detained (usually involving at least an overnight stay) at the hospital or emergency ward for observation and/or treatment that would not have been appropriate in the physician's office or outpatient setting. Complications that occur during hospitalization are AEs. If a complication prolongs hospitalization or fulfills any other serious criteria, the event is serious. When in doubt as to whether "hospitalization" occurred or was necessary, the AE should be considered serious.

Hospitalization for elective treatment of a pre-existing condition that did not worsen from baseline is not considered an AE.

- **Results in persistent or significant disability/incapacity**

Disability means substantial disruption of the participant's ability to conduct normal life functions.

This definition is not intended to include experiences of relatively minor medical significance such as uncomplicated headache, nausea, vomiting, diarrhea, influenza, and accidental trauma (e.g., sprained ankle) which may interfere with or prevent everyday life functions but do not constitute a substantial disruption.

- **Is a congenital anomaly/birth defect.**

- **Other significant events:**

Medical or scientific judgment should be exercised in deciding whether SAE reporting is appropriate in other situations such as important medical events that may not be immediately life-threatening or result in death or hospitalization but may jeopardize the participant or may require medical or surgical intervention to prevent one of the other outcomes listed in the above definition. These events should usually be considered serious.

Examples of such events include invasive or malignant cancers, intensive treatment in an emergency room or at home for allergic bronchospasm, blood dyscrasias or convulsions that do not result in hospitalization, or development of drug dependency or drug abuse.

3. RECORDING OF ADVERSE EVENT AND/OR SERIOUS ADVERSE EVENT

When an AE/SAE occurs, it is the responsibility of the Investigator to review all documentation (e.g., hospital progress notes, laboratory reports, and diagnostics reports) related to the event.

The Investigator will then record all relevant AE/SAE information in the eCRF.

It is **not** acceptable for the Investigator to send photocopies of the participant's medical records to Medical Monitor in lieu of completion of the eCRF.

There may be instances when copies of medical records for certain cases are requested by Sponsor's Medical Monitor. In this case, all participant identifiers, with the exception of the participant number, will be redacted on the copies of the medical records before submission to Sponsor's Medical Monitor.

The Investigator will attempt to establish a diagnosis of the event based on signs, symptoms, and/or other clinical information. Whenever possible, the diagnosis (not the individual signs/symptoms) will be documented as the AE/SAE.

